#### 9.1.2 Relationship to Study Drug

The relationship of each AE to the investigational product should be determined by the investigator using these explanations:

- *Definite*: When there are good reason and sufficient documentation to demonstrate a direct causal relationship between investigational product and AE;
- *Probable*: When there are good reasons and sufficient documentation to assume a causal relationship in the sense of plausible, conceivable, likely but not necessarily highly probable.

- *Possible*: When there is sufficient information to accept the possibility of a causal relationship in the sense of not impossible and not unlikely, although the connection is uncertain or doubtful, for example; due to missing data or insufficient evidence.
- *None*: When there is sufficient information to accept a lack of a causal relationship, in the sense of impossible and improbable.
- *Unclassified*: When the causal relationship is not assessable for whatever reason due to insufficient evidence, conflicting data or poor documentation.

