mmHg	Millimeters of Mercury
OD	Right Eye
OPI	Ocular Protection Index
OS	Left Eye
OSDI [®]	Ocular Surface Disease Index
OU	Both Eyes
OTC	Over-the-counter
PMNs	Polymorphonuclear Leucocytes
PP	Per Protocol
PT	Preferred Term
TID	Three Times a Day
SAE	Serious Adverse Event
SAP	Statistical Analysis Plan
SDC	Statistics and Data Corporation
SOC	System Organ Class
SOP	Standard Operating Procedure
TFBUT/TBUT	Tear Film Break-up Time
TEAE	Treatment Emergent Adverse Event
VA	Visual Acuity
VAS	Visual Analogue Scale
WHO	World Health Organization

1. Introduction

The purpose of this statistical analysis plan (SAP) is to describe the planned analyses and reporting for protocol TOP1630-TV-04, version 2.0 dated 20Jan2017.

This SAP is being written with due consideration of the recommendations outlined in the most recent International Conference on Harmonization (ICH) E9 Guideline entitled Guidance for Industry: Statistical Principles for Clinical Trials and the most recent ICH E3 Guideline, entitled Guidance for Industry: Structure and Content of Clinical Study Reports (CSR).

This SAP describes the data that will be analyzed and the subject characteristics, efficacy, and safety assessments that will be evaluated. This SAP provides details of the specific statistical methods that will be used. The statistical analysis methods presented in this document will supersede the statistical analysis methods described in the clinical protocol. If additional analyses are required to supplement the planned analyses described in this SAP they may be completed and will be identified in the CSR.

2. Study Objectives

The primary objective of this study is to compare the safety and tolerability of TOP1630 Ophthalmic Solution to placebo. The secondary objectives are to compare the efficacy of TOP1630 Ophthalmic Solution to placebo for the treatment of the signs and symptoms of dry eye syndrome.

3. Study Variables

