14.1 Adverse Events

An AE is defined as any untoward medical occurrence associated with the use of an investigational product (IP) in humans, whether or not considered IP-related. TEAEs are defined as AEs that occur after the first use of IP. Per the protocol, only AEs that begin or worsen after receipt of the first dose of IP will be captured in the database for this study; therefore, TEAEs and AEs are equivalent in this study and will be denoted as AEs. All AEs will be assigned a severity grade of mild, moderate, or severe. Their relationship to IP will be classified as suspected (definite, probable or possible) or not suspected (not related). The expectedness of an AE will be classified as unexpected, expected or not applicable. Documentation of AEs will include onset date, severity, action(s) taken, IP relationship, expectedness, outcome, resolution date, and seriousness. All AEs will be coded using MedDRA classifications with reference to SOCs and PTs (MedDRA version 20.0).

An adverse event is considered serious if, in the view of either the investigator or sponsor, it results in any of the following outcomes:

- Death;
- A life-threatening AE;
- Inpatient hospitalization or prolongation of existing hospitalization;
- A persistent or significant incapacity or substantial disruption of the ability to conduct normal life functions;
- A congenital anomaly/birth defect.

Important medical events that may not result in death, be life-threatening, or require hospitalization may be considered serious when, based upon appropriate medical judgment, they may jeopardize the subject and may require medical or surgical intervention to prevent one of the outcomes listed above.

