An overall tabular summary of AEs will be presented that includes the number of events and the number and percentage of subjects who experienced at least one event, by treatment group and overall. This summary will also include breakdowns of AEs further categorized as ocular or non-ocular, SAEs, AEs by maximal severity, AEs leading to subject withdrawal and AEs resulting in death. Additional summaries of AEs will be provided showing the number and percentage of subjects who experienced at least one AE, separately for ocular and non-ocular AEs. Ocular and non-ocular AEs will be summarized separately using discrete summary statistics and presented by treatment group at the subject and event level by SOC and PT using the Safety population. If a subject reports the same PT multiple times within the same SOC, that PT will only be reported once within that SOC. As with the PT,

if a subject reports multiple conditions within the same SOC, that SOC will only be reported once. The occurrence of AEs suspected to be related to IP will also be tabulated by SOC and PT, separately for ocular and non-ocular events. SAEs will also be summarized separately for ocular and non-ocular events. All AEs will be presented in a listing.

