14.2.5	Lissamine Green Staining (NEI Scale)	miITT Population
14.2.6	Tear Film Break-up Time (TFBUT)	miITT Population
14.2.7	Conjunctival Redness	miITT Population
14.2.8	Lid Margin Redness	miITT Population
14.2.9	Posterior Lid Edge Evaluation	miITT Population
14.2.10	Unanesthetized Schirmer's Test	miITT Population
14.2.11	Ora Calibra® Drop Comfort Scale	miITT Population
14.2.12	Ora Calibra® Drop Comfort Questionnaire	miITT Population
14.2.13	Ocular Surface Disease Index (Pre-CAE®)	miITT Population
14.2.14	Ora Calibra® Ocular Discomfort & 4-Symptom Questionnaire	miITT Population
14.2.15	Ocular Symptoms – Visual Analog Scale (VAS)	miITT Population
14.2.16	Ora Calibra® Ocular Discomfort Scale during CAE®	miITT Population
14.2.17	Diary Assessments	miITT Population
14.2.18	Ocular Protection Index (OPI) 2.0	miITT Population
Safety Analyses		
14.3.1.1	Overall Adverse Event Summary	Safety Population
14.3.1.2	All Ocular Adverse Events	Safety Population
14.3.1.3	All Non-Ocular Adverse Events	Safety Population
14.3.1.4	All Ocular Adverse Events Suspected to be Related to Investigational Product	Safety Population
14.3.1.5	All Non-Ocular Adverse Events Suspected to be Related to Investigational Product	Safety Population
14.3.1.6	All Ocular Serious Adverse Events	Safety Population
14.3.1.7	All Non-Ocular Serious Adverse Events	Safety Population
14.3.2	Visual Acuity (logMAR)	Safety Population
14.3.3.1	Slit Lamp Biomicroscopy	Safety Population
14.3.3.2	Slit Lamp Biomicroscopy – Shift Table	Safety Population
14.3.4	Intraocular Pressure (mmHg)	Safety Population
14.3.5.1	Undilated Fundoscopy	Safety Population
14.3.5.2	Undilated Fundoscopy – Shift Table	Safety Population
14.3.6	Corneal Sensitivity (Cochet-Bonnet)	Safety Population

Table Number	Title	Population
14.3.7	Compliance with Study Drug	miITT Population
14.3.8	Exposure to Study Drug	miITT Population
14.3.9	Vital Signs	Safety Population

22. Listings

Listing Number	Title	POPULATION
16.1.7	Randomization Schedule	All Randomized Subjects
16.2.1	Subject Disposition	All Randomized Subjects
16.2.2.1	Protocol Deviations	All Randomized Subjects
16.2.2.2	Inclusion and Exclusion Criteria	All Randomized Subjects
16.2.3	Subjects Excluded from the Per Protocol Population	All Randomized Subjects
16.2.4.1	Demographics	All Randomized Subjects
16.2.4.2	Baseline Characteristics	All Randomized Subjects
16.2.4.3	Ocular Medical History	All Randomized Subjects
16.2.4.4	Non-Ocular Medical History	All Randomized Subjects

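### The SAP's suspected / not suspected grouping has no place for the protocol's Unclassified causality grade, so each arm's suspected-AE count can be understated

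*SAP*

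**What the plan says.** Protocol section 9.1.2 (Relationship to Study Drug) sets a five-grade scale: Definite, Probable, Possible, None and Unclassified. Unclassified applies as follows: "When the causal relationship is not assessable for whatever reason due to insufficient evidence, conflicting data or poor documentation".

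SAP section 14.1 (Adverse Events) reduces the scale to two groups: "Their relationship to IP will be classified as suspected (definite, probable or possible) or not suspected (not related"). It then uses the first group to select events for tabulation: "The occurrence of AEs suspected to be related to IP will also be tabulated by SOC and PT, separately for ocular and non-ocular events". In the table list (SAP section 21) these are Table 14.3.1.4, "All Ocular Adverse Events Suspected to be Related to Investigational Product", and its non-ocular counterpart, Table 14.3.1.5.

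Section 14.1 also says: "All AEs will be presented in a listing". SAP section 2 gives the aim that the AE tables serve: "The primary objective of this study is to compare the safety and tolerability of TOP1630 Ophthalmic Solution to placebo".

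**The concern.** The SAP names the members of the suspected group one by one, and Unclassified is not among them. It does not belong in the other group either, because the protocol keeps None for cases where there is enough information to accept that no relationship exists. An event that could not be assessed is the opposite case.

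A programmer who follows the sentence as written would select definite, probable and possible for Tables 14.3.1.4 and 14.3.1.5. An Unclassified event would then be missing from those tables, exactly as if it had been judged unrelated. Safety and tolerability against placebo is the primary objective, and Protocol section 1 says this is the first administration of TOP1630 in man. The count of suspected reactions is therefore a figure that readers will look for. If the rule is not fixed beforehand, the choice could be made in programming after the treatment codes are known.

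**Working it through.** **Step 1. Set the scale beside the grouping.**

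| Protocol 9.1.2 grade | SAP 14.1 group |
|---|---|
| Definite | suspected |
| Probable | suspected |
| Possible | suspected |
| None | not suspected (the SAP's label is not related) |
| Unclassified | no group given |

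Five grades, four placed, one not placed.

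**Step 2. Look for a rule elsewhere.**
- Protocol 10.4.5 asks for frequencies of treatment-related AEs but does not say which grades count.
- SAP 9.2, on missing or inconclusive data, covers efficacy only.
- SAP 1 says that the SAP's methods replace the protocol's, and SAP 18 declares no changes from the protocol.

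The sentence in SAP 14.1 is therefore the only working definition.

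**Step 3. Find where an Unclassified AE is still counted.**
- Tables 14.3.1.1 to 14.3.1.3 (overall, ocular, non-ocular): yes.
- Tables 14.3.1.6 and 14.3.1.7 (serious): yes, if serious.
- Listing 16.2.7.1: yes.
- Tables 14.3.1.4 and 14.3.1.5 (suspected): no, if the rule is applied literally.

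The overall summary described in SAP 14.1 is broken down by ocular or non-ocular, seriousness, severity, withdrawal and death, but not by relationship. No other planned table would show that causality had been left open.

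**Step 4. Reproduce the plan's own safety figure.** SAP section 6 and Protocol 10.3 give a 79% probability of detecting AEs with a rate of 5% or more in either arm. With n = 30 in an arm:

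1 − (1 − 0.05)^30 = 0.785

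This agrees with 79%. Pooling 60 subjects gives 0.954, so the stated figure is per arm. It concerns all AEs and is not affected by the grouping.

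**Step 5. Size per affected subject.** An affected subject is one whose only candidate reaction in a table row is graded Unclassified. With 30 in the arm:
- one subject: 1/30 = 3.3 percentage points, so 1/30 would be reported as 0/30;
- two subjects: 2/30 = 6.7 percentage points, so 2/30 would be reported as 0/30.

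**Step 6. Illustration over an assumed range.** The documents do not give the share u of cases that would be graded Unclassified. Assume a true AE rate of 5%, and that every assessable case is graded as suspected. The chance of at least one case in an arm's suspected table is then 1 − (1 − 0.05 × (1 − u))^30:

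| u (assumed) | Chance of at least one case |
|---|---|
| 0% | 78.5% |
| 10% | 74.9% |
| 20% | 70.6% |
| 30% | 65.7% |
| 50% | 53.2% |

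**The case against.** The strongest reply is that little depends on these two tables. The comparison with placebo rests first on all-AE incidence by arm, which needs no causality grade and loses no events. SAP section 14 plans no inferential testing of safety, and the study stopping criteria in Protocol 5.3 do not use causality-grouped tables. This stands, and it keeps the severity low.

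Second, Possible already takes many of the uncertain cases. Protocol 9.1.2 describes it as a doubtful connection, for instance where data are missing or evidence is thin, and the SAP counts it as suspected. For serious events, Protocol 9.3.2 also requires a statement on whether the event was suspected to be related. Unclassified may therefore be rare. This stands as a limit on size. The overlap also works the other way: two similar events could receive different grades, and only one would reach the suspected tables.

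Third, the SAP does not say that Unclassified is excluded, and the table shells and eCRF are not in the documents. That is fair. The omission follows from a literal reading of the rule and is not a stated exclusion.

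A reader might infer that the gap makes TOP1630 look safer than placebo. The documents do not support that. Grading is masked (Protocol 8.1.4 and 9.4, SAP 5.2) and the rule applies to both arms. If Unclassified gradings fell more on placebo, leaving them out would make TOP1630 look worse by comparison.

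**Conclusion.** The gap is real, and its severity is low. A stated rule does not cover the protocol's own scale. Applied literally, it can only lower the suspected-AE incidence in each arm, by 3.3 percentage points per affected subject. This assumes 30 subjects per arm in the Safety population and a subject with no other suspected event in the same row. The number of such subjects is unknown and could be zero.

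Two stronger conclusions do not follow. These AEs are not lost from the safety analysis as a whole, and no direction of bias in the comparison with placebo can be claimed. The percentages in the last table of the working depend on an assumed share of Unclassified gradings and are not a forecast.

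**What to change.** Before unmasking, amend the sentence in SAP 14.1 so that the suspected group contains Definite, Probable, Possible and Unclassified, and the not suspected group contains None only. Apply this to Tables 14.3.1.4 and 14.3.1.5. In a footnote or a separate row of each table, give the number graded Unclassified by arm, so that the suspected count can be read with and without them. This also meets the objection that the investigator did not actually record a suspicion for these events. The same sentence could say how a relationship left blank is handled.

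The cost is one phrase in the SAP, one programming condition and one footnote or row. The downside is that suspected-AE counts may be slightly less favourable. Sample size, testing and the other AE tables do not change.

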14.2 Visual Acuity (ETDRS)

VA will be measured at the beginning of every study visit. VA (logMAR) will be summarized at each visit using quantitative summary statistics for both eyes combined by treatment. Qualitative summaries for worsening of acuity of 10 letters or greater from the previous visit will also be tabulated. VA results will be presented in a data listing.

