### **5.3 Withdrawal Criteria and Study Stopping Criteria**

Subjects may withdraw consent from study participation at any time.

If at any time during the study the investigator determines that a subject's safety is or has been compromised, the subject may be withdrawn from the study.

Subjects may be discontinued prior to their completion of the study due to the following safety stopping criteria being met for any subject:

- Persistent loss of 3 or more lines of visual acuity not explained by the condition under investigation and confirmed upon repeat testing
- Development of persistent corneal opacities or severe keratitis
- Persistent ocular irritation or redness not explained by condition
- IOP increase of 12 or more confirmed upon repeat testing
- Sight threatening adverse events such as corneal melting or corneal ulceration;
- Any other possibly related adverse events

Other reasons for discontinuation:

- Protocol violations

- Administrative reasons (e.g., inability to continue, lost to follow up)
- Subject choice (e.g. withdrawal of consent)
- Non compliance
- Any valid medical reason at discretion of investigator (see section 8.6.2)
- Other

Notification of a subject discontinuation and the reason for discontinuation will be made to Ora and/or study Sponsor and will be clearly documented in the eCRF.

Discontinued subjects will not be replaced.

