### **8.4.2 Unscheduled Visits**

These visits may be performed in order to ensure subject safety. All procedures performed at an unscheduled visit will be recorded in the

source documents and on the Unscheduled Visit eCRF pages. Any procedure indicated in the eCRF that is not performed should be indicated as “Not done.”

Evaluations that may be conducted at an Unscheduled Visit include:

- Visual Acuity;
- Slit-lamp Biomicroscopy;
- Intraocular pressure (non-contact);
- Pregnancy Test;
- Undilated Fundoscopy;
- Assessment of Adverse Events;
- Assessment of concomitant medications and/or treatments; and
- Any other assessments needed in the judgment of the investigator.

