### **LogMAR Visual Acuity Calculations**

The last line in which a letter is read correctly will be taken as the base logMAR reading. To this value will be added the number " $N \times 0.02$ " where 'N' represents the total number

of letters missed up to and including in the last line read. This total sum represents the logMAR visual acuity for that eye.

For Example: Subject correctly reads 4 of 5 letters on the 0.2 line, and 2 of 5 letters on the 0.1 line.

Base logMAR	= 0.1
N (total number of letters incorrect on line 0.2 as well as 0.1)	= 4
N x T (T=0.02)	= 0.08
Base logMAR + (N x T)	= 0.1 + 0.08
logMAR VA	= 0.18

Repeat the procedure for the left eye (OS).

In order to provide standardized and well-controlled assessments of visual acuity during the study, all visual acuity assessments at a single site must be consistently done using the same lighting conditions and same correction if possible during the entire study. If the same correction cannot be used (i.e., a subject forgets his/her glasses), the reason for the change in correction should be documented.

Note: A clinically significant visual acuity decrease (defined as an increase of 0.22 or greater in logMAR score) from baseline will be considered an Adverse Event.

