13.2 Treatment Exposure

For the Safety and Efficacy Assessment, extent of exposure will be calculated in days using the following:

Extent of Exposure (days) = [Date of last dose – Date of Visit 2b (Day 1)] + 1

Extent of treatment exposure (days) for each subject exposed to study drug will be summarized with continuous descriptive statistics for each treatment group, using the Safety population. A subject listing of treatment exposure will also be produced.

14. Safety Analyses

Frequencies and percentages of subjects with treatment-emergent adverse events (TEAEs), serious TEAEs, and TEAEs causing discontinuation will be provided by treatment group. An AE is treatment emergent if it occurs or worsens after the first dose of study treatment. Furthermore, frequencies will be given of subjects with TEAEs by SOC and PT; by SOC, PT and maximal severity; by SOC and PT for treatment-related AEs; by SOC, PT for SAEs; and by SOC, PT, and time of onset. Separate summaries will be provided for ocular specific and all AEs (including systemic).

Other safety endpoints including VA, slit-lamp biomicroscopy, corneal sensitivity, undilated fundoscopy, IOP (non-contact), and vital signs will be summarized by treatment group, visit, and time point (where relevant) using descriptive statistics. Changes or shifts from baseline will also be summarized where appropriate. For assessments performed by eye, study eye and fellow eye will be summarized separately. In addition, shifts from baseline to worst on-treatment value for ocular safety assessments will be summarized.

Safety variables will be summarized as appropriate. All safety analyses will be performed on the Safety population. No statistical inferential testing will be performed for safety variables.

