14.6 Intraocular Pressure (IOP)

IOP will be measured at Visits 1b (post-CAE®) and 4b (post-CAE®). IOP will be summarized for both eyes combined by visit and treatment group using quantitative summary statistics. At Visit 4b, an IOP of ≥ 21 mmHg AND ≥ 10 mmHg over baseline (Visit 1b) will be considered an AE, and presented in the tabular summary. Results will be listed for both eyes at each visit.

15. Tolerability Analyses

Two tools will be used to assess drop comfort, each of which will be assessed at Visit 2b (Day 1) and Visit 3b (Day 15 ± 1), following the first dose of study drug.

subject will be used for this analysis. Drop comfort will be summarized using quantitative summary statistics. Statistical comparisons will employ two-sample *t*-tests as the primary method of analysis.

- Ora Calibra® Drop Comfort Questionnaire will be used to assess drop comfort

Drop Comfort Questionnaire responses will be summarized using qualitative summary statistics. Subjects with at least one negative response will also be summarized.

16. Exploratory Efficacy Analyses

The continuous and ordinal secondary efficacy variables collected at each visit will be summarized descriptively (n, mean, SD, median, minimum and maximum), and analyzed with two-sample *t*-tests comparing the active treatment groups to placebo. All visit-based data will be analyzed at each visit as well as change from baseline. A Wilcoxon rank sum test and an ANCOVA model adjusting for baseline will also be assessed where appropriate. Corneal fluorescein staining by region and total (Ora and NEI scales), lissamine green staining by region, TFBUT, conjunctival redness, unanesthetized Schirmer's test, ocular symptoms (Ora Calibra® scales and VAS), OSDI®, ocular discomfort and changes from baseline in these measures will be analyzed by visit and time point, where applicable (i.e., pre- and post-

[figure not shown]
CAE[®]), using two-sample *t*-tests and Wilcoxon rank sum tests. Changes from baseline will also be analyzed using ANCOVA models adjusting for baseline values. For the measures of symptoms during CAE[®], the ANCOVA models will also include the pre-CAE[®] measure as a covariate. Symptoms recorded on the daily diary will be analyzed using repeated measure ANCOVA models, where baseline scores are calculated as the average scores in the run-in period and post-baseline scores are calculated as weekly morning, afternoon, evening, and daily averages.

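### SAP 14.2, 14.4 and 14.6 pool the two eyes although SAP 14 calls for them separately, and the one acuity count in SAP 14.2 runs from the previous visit, so at Visit 4b it can miss an 11 to 18 letter loss from baseline

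*SAP*

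**What the plan says.** **Eyes.** The opening of SAP 14 states: "For assessments performed by eye, study eye and fellow eye will be summarized separately". Protocol 10.4.5 has the same sentence. The endpoint sections then split. SAP 14.3 (slit lamp) and 14.5 (fundoscopy) report worst eye and fellow eye apart. SAP 14.2 (acuity), 14.4 (corneal sensitivity) and 14.6 (intraocular pressure) pool the two eyes. SAP 18 reports no changes from the protocol-stated analyses.

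**Acuity count.** Besides quantitative summaries at each visit, SAP 14.2 specifies one categorical result: "Qualitative summaries for worsening of acuity of 10 letters or greater from the previous visit will also be tabulated". Protocol Appendix 2, under the logMAR calculations, treats a clinically significant decrease differently: it is "defined as an increase of 0.22 or greater in logMAR score) from baseline will be considered an Adverse Event".

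**General provisions that bear on acuity.** SAP 14 names acuity among the endpoints to be summarised, says that changes or shifts from baseline will also be summarised where appropriate, and adds: "In addition, shifts from baseline to worst on-treatment value for ocular safety assessments will be summarized". It gives no category or threshold for acuity. SAP 21 lists one acuity table (14.3.2), whose shell is not shown. SAP 9.3 places baseline at the last measure before treatment, usually Visit 2b.

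**The concern.** Comparing safety and tolerability with placebo is the primary objective, and acuity, corneal sensitivity and intraocular pressure are named safety variables. Two things in their specification do not fit together.

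First, the SAP gives opposite instructions on the same three endpoints: apart in the opening of SAP 14, pooled in 14.2, 14.4 and 14.6. Whoever programs the tables must choose. Pooling also averages a change confined to one eye with the other eye's values.

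Second, the one acuity count stated uses a different reference point and a different threshold from the protocol's own definition of clinically significant loss. A count from the previous visit restarts at each visit, so a decline spread over both treatment intervals need not appear in it, while a return from a temporary gain can. A reader of that row could take it as the number of eyes with meaningful loss on treatment, which it is not.

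**Working it through.** **Eye handling, side by side**

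- SAP 14 (opening) and protocol 10.4.5: study eye and fellow eye apart.
- SAP 14.3 and 14.5: worst eye and fellow eye apart, consistent with SAP 14.
- SAP 14.2, 14.4 and 14.6: the two eyes pooled, in conflict with SAP 14.
- SAP 9.1: safety is analysed for both eyes. This does not say pooled or apart, so it settles nothing.
- SAP 1: "The statistical analysis methods presented in this document will supersede the statistical analysis methods described in the clinical protocol". This ranks the SAP above the protocol, but the conflict lies inside the SAP, so the clause does not resolve it.
- SAP 18: no changes declared. If the pooled wording governs, that statement does not match protocol 10.4.5.

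**Acuity count: inputs**

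- One letter = 0.02 logMAR (protocol Appendix 2). The protocol's worked example reproduces: 0.1 + 4 × 0.02 = 0.18.
- Protocol amount: 0.22 / 0.02 = 11 letters or more, from baseline.
- SAP 14.2 amount: 10 letters or more (10 × 0.02 = 0.20 logMAR), from the previous visit.
- Baseline taken as Visit 2b (SAP 9.3). Acuity is measured at every visit, so the scheduled visits after baseline are 3b and 4b.

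Let a be the loss in letters from 2b to 3b and b the loss from 3b to 4b, with a gain negative.

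**Visit 3b.** The previous visit is the baseline visit. The SAP rule is a ≥ 10 and the protocol amount is a ≥ 11. They differ only at a = 10, and no loss of 11 or more letters is missed.

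**Visit 4b.** A loss from baseline that reaches the protocol amount but is counted at neither visit needs a ≤ 9, b ≤ 9 and a + b ≥ 11. For a total T, a runs from T − 9 to 9, which gives 19 − T pairs:

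- T = 11: 8 pairs
- T = 12: 7
- T = 13: 6
- T = 14: 5
- T = 15: 4
- T = 16: 3
- T = 17: 2
- T = 18: 1

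The sum is 8 + 7 + 6 + 5 + 4 + 3 + 2 + 1 = 36 whole-letter pairs. The missed losses run from 11 letters (for example 2 then 9) to 18 letters (9 then 9), that is, from 11 × 0.02 = 0.22 to 18 × 0.02 = 0.36 logMAR.

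**Opposite error.** With a = −8 and b = 10, the row counts the eye at 4b although the net loss is 10 − 8 = 2 letters, or 2 × 0.02 = 0.04 logMAR.

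**Count from baseline.** With the reference at Visit 2b and a threshold of 11 letters, every total from 11 to 18 is counted at 4b, and the +8 then −10 eye is not.

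**The case against.** The strongest reply is that nothing is lost from the safety record. Appendix 2 makes a loss of 0.22 logMAR or more from baseline an adverse event, so it should be recorded as one, appear in the adverse event tables by arm and be listed. The acuity values are listed too. This stands, and it is why the point is minor. It does not make the 10-letter row informative, because adverse event tables are organised by system organ class and preferred term and do not count measured acuity against a threshold.

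Next, SAP 14 already promises changes or shifts from baseline, and SAP 14.2 presents its count as an addition to the other summaries. This also stands in part. The absence of a listed acuity shift table proves little: SAP 16.4 specifies change from baseline for tear film break-up time, yet only one table is listed for it. Table 14.3.2 may contain baseline changes. What remains is that no acuity category from baseline is stated anywhere in the SAP.

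On the eyes, one can say that the endpoint sections are specific and govern over the general opening. That is a reasonable reading, but the SAP states no such rule, and it would leave SAP 18 inaccurate against protocol 10.4.5.

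Some stronger readings are tempting and should be resisted.

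- A reader might infer that SAP 14.6 shows the SAP handling intraocular pressure better, since a rise "over baseline (Visit 1b) will be considered an AE, and presented in the tabular summary". That summary may simply be the overall adverse event table of SAP 14.1, the route an acuity event also takes. Pressure is also scheduled only at Visits 1b and 4b, so no previous-visit problem can arise.
- A reader might link the larger missed losses to the withdrawal criterion "Persistent loss of 3 or more lines of visual acuity". That criterion also requires that the loss is not explained by the condition and is confirmed on repeat testing. One reading at 4b does not establish this.
- A reader might extend the gap to missed or unscheduled visits. SAP 4.1 labels visits in tables by expected study day, which points to scheduled visits.

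**Conclusion.** Both parts hold as minor faults of specification.

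1. SAP 14.2, 14.4 and 14.6 contradict the opening of SAP 14 on whether the eyes are pooled, and SAP 18 does not declare the pooling as a departure from protocol 10.4.5.
2. The only categorical acuity count stated in SAP 14.2 does not follow the protocol's definition of clinically significant loss. At Visit 3b the difference is a single letter. At Visit 4b the row can miss losses of 11 to 18 letters (36 whole-letter pairs) and can count an eye with a net loss of only 2.

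This rests on whole-letter scoring, baseline at Visit 2b, acuity measured at the scheduled Visit 3b, and the same eye followed throughout. The 36 pairs are arithmetic possibilities, not subjects or probabilities. A miss rate would depend on how losses divide between the two intervals and on measurement error, and the documents give neither, so the number of subjects affected cannot be derived.

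A reader might infer that clinically significant acuity loss would go unreported, or that a comparison between arms would be biased. The documents support neither: adverse event reporting is separate from this row, and SAP 14 plans no inferential testing of safety variables. Because the shell of Table 14.3.2 is not shown, only the 10-letter row is shown to be deficient, not the whole table.

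**What to change.** - **Eyes.** In SAP 14.2, 14.4 and 14.6, summarise study eye and fellow eye separately, as SAP 14.3 and 14.5 already do. Alternatively, amend the opening of SAP 14 to allow pooling for these three endpoints and list the departure from protocol 10.4.5 in SAP 18.
- **Acuity.** In SAP 14.2, add a count of worsening from baseline (Visit 2b) at Visits 3b and 4b and at the worst on-treatment value, using the protocol's existing 0.22 logMAR definition. The previous-visit 10-letter row may stay beside it. No new clinical threshold is needed.

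The cost is SAP wording and table shells. Acuity and intraocular pressure are already measured in each eye and corneal sensitivity is already listed for both eyes, so no further data collection is required.
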